4.1.2 Censoring Scheme

Primary Censoring Scheme: for time-to-event endpoints, patients will be censored at the earliest of: 1) end of study date, and 2) date of dialysis status change.

End of study date is defined as the earliest of:

- date of withdrawal from study
- date of lost to follow-up
- date of study completion

Date of dialysis status change is the earliest of the following:

- date of transfer to another dialysis facility
- date of kidney transplantation
- date of transfer to peritoneal dialysis
- date of withdrawal from dialysis

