#### Status change: all

- Date of transfer to another dialysis facility
- Date of kidney transplantation
- Date of transfer to peritoneal dialysis
- Date of withdrawal from dialysis
- Date of death

The study team will also be collecting and transmitting patient reported outcomes (as well as name and phone number for patients that wish to complete the surveys via telephone) to Northwestern University.

- Kidney Disease and Quality of Life (KDQOL™-36)
- PROMIS Gastrointestinal Belly Pain 5a
- PROMIS Gastrointestinal Constipation 9a
- PROMIS Gastrointestinal Diarrhea 6a
- PROMIS Gastrointestinal Gas and Bloating 13a

- PROMIS Gastrointestinal Nausea and Vomiting 4a
- Name
- Phone Number

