#### 5.5 Participant Withdrawal

Participants may decide to withdraw from the study at any time. Patients who initially participate but later elect to withdraw from the trial will have no data transmitted to the DCRI after the date of withdrawal. Additionally, participants who increase dialysis frequency to more than three times weekly, including participants in the high arm who become pregnant, will be withdrawn from the study by the dialysis provider.

Data transmitted to the DCRI prior to withdrawal will remain in the trial database. Contact information for the research personnel from the relevant dialysis provider organization will be available at participating dialysis facilities throughout the duration of the trial to facilitate communication such as a decision to withdraw from the trial. Participants who elect to discontinue phosphate binder medications or protocol-based treatment algorithms will remain as trial participants and continue to have data transmitted to the DCRI unless they withdraw from the trial.

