## 8.2 Statistical Design

In the primary analysis of efficacy, the intention to treat (ITT) sample will be used that includes all randomized patients.

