## 8.3 **Primary Outcome Analysis**

The primary outcome for HiLo is the hierarchical composite endpoint of time to all-cause mortality and the all-cause hospitalization rate in that order. Participants will have a rank score calculated using all pairwise comparisons and subsequently tested by the method proposed by Finkelstein and Schoenfeld. Participants will be hierarchically compared first on time to all-cause mortality, and compared on hospitalization rate only if the mortality comparison is not possible (e.g., both participants in an individual comparison survive throughout the follow-up period).

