3. STUDY ENDPOINTS

3.1 Primary Endpoint

The primary outcome for HiLo is the hierarchical composite of: 1) time to all cause death followed by 2) number of all cause hospitalizations. The use of this endpoint will allow for simultaneous testing of both mortality and hospitalizations while prioritizing mortality as the more important health outcome to consider. Time zero for the time to all cause death portion of the endpoint will be the date of the first dialysis session after the patient has consented to participate in HiLo.

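### Deaths after a participant stops dialysis are left out of the all-cause mortality tier and the Cox model, and no sensitivity analysis counts them

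*SAP*

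**What the plan says.** SAP 3.1 defines the primary endpoint as "1) time to all cause death followed by 2) number of all cause hospitalizations". Protocol 8.2 says that for the primary analysis "the intention to treat (ITT) sample will be used that includes all randomized patients".

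SAP 4.1.2, under the label "Primary Censoring Scheme", states that for time-to-event endpoints "patients will be censored at the earliest of: 1) end of study date, and 2) date of dialysis status change". Four dates count as a dialysis status change: transfer to another facility, kidney transplantation, transfer to peritoneal dialysis, and "date of withdrawal from dialysis". Withdrawal from the study is listed separately, under the end of study date. The last of the four therefore most naturally means that dialysis itself was stopped.

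SAP 4.5.1 decides a pair on death only if one patient's death is observed before the other is censored. Otherwise the pair is compared on hospitalization counts up to the earlier censoring time. The Cox model in SAP 4.5.2 has no censoring rule of its own.

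Protocol 5.4 extracts "Date of withdrawal from dialysis" and the date of death. Protocol 5.5 stops data transfer for participants who "elect to withdraw from the trial will have no data transmitted to the DCRI after the date of withdrawal". It does not say that transfer stops when dialysis stops.

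**The concern.** Read together, these sections mean that a death after dialysis is stopped is not an event. That participant can never lose a comparison on death, yet can still win one against someone who died earlier. Pairs that the death would have decided go to hospitalization counts. What is analysed is death before a dialysis status change, which is narrower than the endpoint's name.

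No other analysis repairs this:
- The label in 4.1.2 implies a second censoring scheme, but none is defined.
- The COVID-19 and away-from-site analyses in SAP 4.5.3 remove further deaths.
- The in-range repeat changes the population, not the rule.
- Protocol 4.7.2 and 5.5 keep following participants who leave their arm, their binders or the algorithm, but neither deals with stopping dialysis.
- SAP section 6 reports no change from the protocol, although Protocol 8.3 and 8.4 do not mention this censoring.

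Three things are at stake. Mortality power falls. Primary power may fall, depending on how much of the effect mortality carries. Both analyses would be biased if the share of deaths that follow dialysis withdrawal differs by arm. The censoring is probably informative, but the documents give no rates.

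**Working it through.** **Inputs.** Protocol 8.1: 3,800 participants, 15% annual mortality in Lo, hazard ratio 0.85, 5% annual loss, 35% not susceptible to hospitalization, 1.8 versus 1.53 hospitalizations per year in the rest. SAP 1.3: 1:1 allocation, censoring uniform over 2 to 4 years, 15% versus 12.8% mortality, 2 versus 1.89 hospitalizations per year. SAP 4.1: two-sided 0.05. The share w of deaths that follow dialysis withdrawal is an assumption throughout.

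**1. Reproduce the stated mortality power (at least 80%).**
Deaths per arm = 1900 × λ/(λ+δ) × (1 − E[exp(−(λ+δ)T)]), with T uniform on 2 to 4 years.
- λ in Lo = −ln(0.85) = 0.1625; in Hi it is 0.85 times that; δ = −ln(0.95) = 0.0513.
- Lo: 1900 × 0.3568 = 678. Hi: 1900 × 0.3137 = 596. Total 1,274.
- Schoenfeld power = Φ(√1274/2 × 0.1625 − 1.96) = Φ(0.94) = 82.6%. The stated figure is reproduced.

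**2. How many deaths can be lost.**
Deaths needed for 80% = 4 × ((1.96 + 0.8416)/ln 0.85)² = 1,189. Break-even share = 1 − 1189/1274 = 6.7%. At w = 10%, 20% and 30%, power is 78.6%, 73.7% and 68.0%.

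| Reading of the inputs | Deaths | Break-even share |
|---|---|---|
| 15% annual mortality, as above | 1,274 | 6.7% |
| 15% and 5% read as yearly hazards (80.3% power) | 1,197 | 0.7% |
| Half of the 5% loss is already dialysis withdrawal | 1,321 | 10.0% |
| All of the 5% loss is already dialysis withdrawal | 1,369 | 13.1% |
| Follow-up of 27 to 45 months (Protocol 4.4) | 1,279 | 7.0% |
| 17.5% annual mortality (Protocol 1.1 gives 15–20%) | 1,452 | 18.1% |
| 20% annual mortality | 1,621 | 26.7% |
| SAP mortality inputs, HR = ln 0.872/ln 0.85 = 0.843 (86.2% power, 1,073 deaths needed) | 1,270 | 15.5% |

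If the 15% already means deaths seen under this censoring scheme, nothing is lost.

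**3. Primary test, equal shares in both arms.** The score and variance of SAP 4.5.1 were simulated with 1,000 trials per scenario, Poisson hospitalizations, and dialysis withdrawal assumed 10 days before death.
- Protocol inputs: 99.3% power without this censoring, 99.5% at w = 10%, 99.1% at w = 25%. No loss is shown.
- SAP inputs: 88.4% without this censoring, then 86.6%, 82.3% and 80.3% at w = 10%, 20% and 25%. The paired changes are −1.8, −6.1 and −8.1 points (SE 0.7, 0.9, 1.1).
- SAP inputs at w = 20%, with deaths counted to 90 days after withdrawal: back to 88.4%.
- No true effect, w = 20% in both arms: 4.3% false rejection.

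A second simulation, coded separately and using a hazard ratio of 12.8/15 = 0.853 with 300 to 500 runs, gave 87% on SAP inputs with all deaths counted, then 86%, 84% and 76% at w = 10%, 20% and 30%.

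**4. Unequal shares.** The mortality hazard ratio is multiplied by about (1 − w in Hi)/(1 − w in Lo). Purely as an illustration, 15% in Lo and 25% in Hi give 0.75/0.85 = 0.88. With no true effect and those shares, 300 simulated trials gave a mean hazard ratio of 0.88; Cox rejected in 53% and the primary test in 33%, all favouring Hi. The reverse split would favour Lo.

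**The case against.** **Names.** All-cause describes the cause of death, and every censored analysis counts only the deaths it observes. ITT defines who is analysed, not how long they are followed. Protocol 8.3 offers its case, where "both participants in an individual comparison survive throughout the follow-up period", only as an example. This stands as far as it goes: there is no flat contradiction. It does not explain why a death whose date is in the extract should be left out.

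**Data source.** Outcomes come from provider records, and SAP 1.3 already treats related departures as loss, so the rule may be deliberate. No section says how completely deaths are recorded after dialysis stops. This stands and limits the fix: following people beyond reliable capture would score unrecorded deaths as survival.

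**Partial visibility.** SAP 4.3.1 will report status changes by arm. That helps, but it promises no split by type and no later deaths.

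**Size.** The share is unknown, and the break-even ranges from 0.7% to 26.7%. The primary loss appears on only one of two differing input sets, and that simulation starts at 88.4%, where SAP 1.3 states more than 95%. From a 95% start, the same proportional losses of signal would cost about 1.1, 4.0 and 5.5 points at w = 10%, 20% and 25%, not 1.8, 6.1 and 8.1. This stands. The exact figures should not be leaned on; the direction is secure.

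**Bias.** It needs unequal shares, for which there is no evidence. That also stands.

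**Conclusion.** The concern holds and should be fixed. As written, the SAP leaves deaths after dialysis withdrawal out of the mortality tier and the Cox model, and no planned analysis counts them.

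With equal shares, the cost is power, not error rate. Mortality loses its stated 80% above a 6.7% share on protocol inputs and above 15.5% on SAP inputs. The primary test loses nothing visible on protocol inputs and several points on SAP inputs, where mortality carries more of the effect. Bias is possible but not shown.

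All sizes rest on an assumed share, and the primary-test figures also rest on Poisson counts and a 10-day gap. Confidence is medium, because neither the share nor the completeness of death capture is documented.

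**What to change.** For the primary and main secondary analyses:

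1. **SAP 4.1.2.** Do not censor death at withdrawal from dialysis. Count later deaths up to one fixed cut-off, the same in both arms, within which both providers confirm that deaths are captured. Otherwise censor at that cut-off or the end of study date, whichever is earlier. State that stopping dialysis is not loss to follow-up.
2. **SAP 4.5.1.** If hospitalization counts stop at dialysis withdrawal, compare counts only to the earlier of the two patients' hospitalization end dates. Otherwise a frozen count is compared with one still accruing. Over an assumed 90 days the other patient would add about 0.65 × 1.8 × 90/365.25 = 0.29 hospitalizations on protocol inputs.
3. **Sensitivity and reporting.** Keep the present scheme as a sensitivity analysis. Report dialysis withdrawals, and deaths after them, by arm.

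A lesser point concerns facility transfer, transplantation and transfer to peritoneal dialysis. Count deaths while the provider's warehouse still reports the participant, at least as a sensitivity analysis. State that a temporary transfer with a return date is not a censoring event, so that 4.1.2 agrees with the away-from-site analysis in 4.5.3.

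The cost is revised wording in two SAP sections, including a second follow-up end date in 4.5.1, one check of death capture with the two providers, and one more sensitivity run. The dates are already in the extract. The downside is that some follow-up will be off the assigned target, and only deaths within confirmed capture can be counted. If capture proves poor, justify the present rule and name the endpoint for what it measures.

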4.2 Study Conduct

Major protocol deviations will be identified for all patients who are randomized (see Section 2.2)

4.3 Study Population

4.3.1 Patient Disposition

The number of patients included in each study population will be summarized by treatment group. The number and percentage of patients who completed, patients who had a change in status, and patients who withdrew from the study or were lost to follow-up will be presented for each treatment group and overall for the ITT population.

4.3.2 Demographics and Other Baseline Characteristics

Demographics and baseline characteristics will be summarized by treatment group for the ITT population. The following demographics and baseline characteristics will be summarized:

- Age
- Sex
- Race
- Ethnicity
- Height
- Weight
- Dialysis vintage
- Co-morbid illnesses noted on admission to the dialysis facility (using ICD-9/10 codes)
- Cause of end-stage renal disease
- Medication use, specifically including phosphate binders and activated vitamin D

4.4 Application of Study Treatment

4.4.1 Treatment Adherence

Serum phosphate will be monitored throughout the trial. Participants are anticipated to have phosphate levels measured at the site at least once per month. The participant monthly average phosphate level and the site level average of the patient average will be monitored for each site to ensure that the site assignment to a phosphate target has the intended effect of changing the patients' phosphate levels. The patient monthly average will be the average of all phosphate measures in a calendar month. The target ranges for patients and site average for each arm are provided in Table 1. Sites will be provided a listing of patient IDs of patients falling outside of the "In range" range will be provided monthly.

Target phosphate (mg/dL)	Hi	Lo
In range	>6.5	<5.5
Near range	5.5 - 6.5	5.5 - 6.5
Out of range	<5.5	>6.5

Table 1. Phosphate target ranges for Hi and Lo arms.

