## 4.5 Randomization

Following consent, patients will be randomized in a 1:1 ratio to the two treatment arms. The randomization will be stratified by site in random sized blocks.

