### 4.6 Intervention

Two phosphate titration protocols will be used that have the same "look and feel" as those used in practice in an effort to sustain a mean time-averaged difference in serum phosphate between the two arms of  $\geq 1 \text{ mg/dl}$ :

- 1. Low serum phosphate target that is consistent with current standard of care: The goal is to titrate and maintain serum phosphate to <5.5 mg/dl.
- Higher serum phosphate target that is the intervention strategy: The goal is to titrate and maintain serum phosphate to ≥6.5 mg/dl by setting a serum phosphate threshold >7.0 mg/dl when binders will be initiated, as has been done previously.

A mean serum phosphate of 4.8–5.2 is anticipated in the low arm and 6.5–6.8 in the high arm, as observed in two pilot clinical trials. Since serum phosphate is 4–7 mg/dl in most patients with ESRD,  $\geq$ 1 mg/dl difference equates with a  $\geq$ 33% difference within the modifiable range of time-averaged phosphate exposure. Specific binder choices will be relegated to the discretion of local providers based on local practice.

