## 8.5.1 Interim Analyses

One interim analysis will be completed when 50% of patients have been enrolled and have at least 24 months of median follow-up time accrued to assess efficacy on the primary outcome. Throughout the trial, the mean separation in serum phosphate between the treatment groups will be continuously monitored, targeting a mean separation of at least 0.75 mg/dL and ideally, a mean separation of at least 1.0 mg/dL.

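### SAP 4.4.1 still checks a site-level average phosphate against a site assignment; at individually randomized sites that average does not identify the Hi-minus-Lo difference

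*SAP*

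**What the plan says.** SAP 4.4.1 names two quantities to follow, "The participant monthly average phosphate level and the site level average of the patient average", and says they "will be monitored for each site to ensure that the site assignment to a phosphate target has the intended effect". It adds: "The target ranges for patients and site average for each arm are provided in Table 1". In that table a value above 6.5 mg/dl is In range for Hi and a value below 5.5 is In range for Lo; 5.5 to 6.5 is Near range for both. Each month the site also receives a list of the patients who are not In range.

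Protocol 4.5 describes a different unit of assignment: "Following consent, patients will be randomized in a 1:1 ratio to the two treatment arms". It continues: "The randomization will be stratified by site in random sized blocks". Protocol 5.3 explains that 30 units (14 Hi, 16 Lo) were randomized as clusters, that their patients stay in the study, and that about 3,800 more participants are to be randomized individually. SAP 4.5.3 itself places site-level randomization under a previous protocol.

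Separation is also followed elsewhere. Protocol 8.5.1 says that throughout the trial "the mean separation in serum phosphate between the treatment groups will be continuously monitored", with goals of 0.75 and ideally 1.0 mg/dl. SAP 4.7 sets the separation futility criterion between arms at 0.75 mg/dl. Protocol 1.2 (item 5) plans automated checks by randomization group and by individual participant.

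**The concern.** Both the site average and its stated purpose belong to the cluster design, in which every participant at a facility shared one target and the facility mean showed whether that target was being delivered. With both arms in one facility, the mean blends two groups that are meant to move apart. It then no longer answers the question it was written for, and with both arms present the SAP does not say which Table 1 column applies to it.

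What is at stake is site follow-up. Protocol 4.8 directs remediation at sites. A site summary that looks the same with and without separation, or better without it, gives poor guidance on where to send that effort.

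**Working it through.** **Inputs.** Protocol 4.6: "A mean serum phosphate of 4.8–5.2 is anticipated in the low arm and 6.5–6.8 in the high arm" (mg/dl; midpoints Lo 5.0, Hi 6.65). Protocol 4.5: allocation 1:1 within site. SAP Table 1: the ranges above. Protocol 5.3 and synopsis: about 3,800 individually randomized of about 4,400, and 30 cluster units.

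**1. The plan's own figure.** Protocol 4.6 says "Since serum phosphate is 4–7 mg/dl in most patients with ESRD" and equates a difference of at least 1 mg/dl with at least 33% of the modifiable range: 1/(7 − 4) = 33.3%, which reproduces. The anticipated means imply a separation of 6.5 − 5.2 = 1.3 to 6.8 − 4.8 = 2.0 mg/dl, consistent with that goal.

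**2. Site average under full separation.** With Hi share f, the average is M = f × Hi + (1 − f) × Lo. At f = 0.5, M runs from (4.8 + 6.5)/2 = 5.65 to (5.2 + 6.8)/2 = 6.00. Table 1 calls all of this Near range for both arms. At the midpoints, M stays in Near range for f = 0.4 (5.66) and f = 0.6 (5.99), so modest imbalance does not alter the reading.

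**3. What M says about separation.** At f = 0.5, any difference D fits a given M, with Lo = M − D/2 and Hi = M + D/2. Using the midpoints:

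| Situation | Lo mean | Hi mean | Hi − Lo | Site average | Lo column | Hi column |
|---|---|---|---|---|---|---|
| Full separation | 5.00 | 6.65 | 1.65 | 5.825 | Near | Near |
| Separation of 0.75 | 5.45 | 6.20 | 0.75 | 5.825 | Near | Near |
| None, at midpoint | 5.825 | 5.825 | 0 | 5.825 | Near | Near |
| Arms reversed | 6.65 | 5.00 | −1.65 | 5.825 | Near | Near |
| None, all at Lo mean | 5.00 | 5.00 | 0 | 5.00 | In | Out |
| None, all at Hi mean | 6.65 | 6.65 | 0 | 6.65 | Out | In |

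The first four rows cannot be told apart. The last two move the average, and each unseparated site then reads as In range in one column, which a fully separated site never does.

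**4. By-arm means.** Full separation gives 5.0 (In range for Lo) and 6.65 (In range for Hi), a difference of 1.65; no separation gives 0.

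**5. Precision at one site.** This part rests on assumptions, because the documents give no SD and no count of individually randomizing sites. Take 70 to 150 sites: the lower end is 100 − 30, the upper end is the planned maximum. Participants per site are then 3,800/150 = 25 to 3,800/70 = 54. With SE = SD × √(4/n) and power = Φ(Δ/SE − 1.96), two-sided 0.05:

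| Assumed SD (mg/dl) | Power for 1.65 | Power for 0.75 |
|---|---|---|
| 1.0 | 0.99 to >0.99 | 0.47 to 0.79 |
| 1.5 | 0.79 to 0.98 | 0.24 to 0.45 |
| 2.0 | 0.55 to 0.86 | 0.16 to 0.28 |

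One site can often show the full anticipated contrast but cannot reliably be judged against 0.75.

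**6. Cluster-phase share.** About 4,400 − 3,800 = 600 participants, or 600/4,400 = 14%, entered under cluster randomization, where the single site average keeps its meaning.

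**The case against.** The strongest reply is that the same paragraph already covers the practical risk. No value is In range for both arms. At a site where everyone sits at one common value, the monthly listing therefore contains at least one whole arm, about half the site, and at 5.825 it contains everyone. A well-separated site would list far fewer. This stands. What the listing does not give is a defined summary by site and arm, so it limits the harm without repairing the site average.

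Second, the sentence introducing Table 1 could be read as a site average computed separately for each arm, which would work. The text leaves room for this, but the SAP defines the average with no split by arm and ties it to a site assignment. If by-arm means were intended, a clarifying sentence settles it.

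A reader might also draw stronger conclusions that the documents do not support:

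- *The trial cannot see lost separation, or its futility criterion is compromised.* Protocol 1.2 and 8.5.1 and SAP 4.7 all work between arms, and no efficacy analysis uses the site average.
- *Every site holds both arms.* This is not shown for the 30 cluster-phase units.
- *The average never moves when separation fails.* It drops to 5.0 if all patients sit at the Lo mean. The shift still cannot be attributed to lost separation, because a site's underlying mean is unknown.
- *Dietitians treating both arms alike is the known main risk of the redesign.* It is conceivable, since Protocol 4.7.1 has facility dietitians carry out the protocols. However, Protocol 5.3 gives biased enrollment as the reason for the change and says nothing about blurred arms.

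**Conclusion.** The point holds for one element of the monitoring plan. SAP 4.4.1 checks a site assignment that individually randomized sites do not have, using an average that does not identify Hi minus Lo. A site performing as anticipated would read 5.65 to 6.00 mg/dl, Near range for both arms, and a site with no separation can read the same or look better in one column.

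This rests on the protocol's anticipated means, on allocation close to 1:1 at each site, and on reading the site average as pooled, which the wording favours without stating it outright. The effect is on directing site follow-up. The trial's error rates, power, and trial-level view of separation are unaffected.

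**What to change.** In SAP 4.4.1:

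- Replace the reference to site assignment with participant assignment.
- For individually randomized sites, report the site mean by arm, each read against its own Table 1 column, and the Hi-minus-Lo difference. Cumulate both over months and use them as a descriptive flag for site follow-up.
- Keep the 0.75 and 1.0 mg/dl separation goals at trial level, where the protocol sets them.
- Keep the single site average only for the 30 cluster-phase units.

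In the protocol, sections 4.6.5, 4.6.6, 4.7.2 and 4.8 still speak of facilities as the randomized unit or of a facility's assignment. They should be reconciled with 4.5, with separate wording for the cluster-phase units where that is meant.

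The cost is one reprogrammed monitoring report from phosphate data already transferred monthly (Protocol 5.4), plus text edits. The downside is that differences at small sites will be noisy, so they should prompt a look at the site and not serve as a pass-or-fail test.

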## PROTOCOL VERSION AND AMENDMENT TRACKING

Protocol Title	HiLo: Pragmatic trial of higher vs lower serum phosphate targets in patients undergoing hemodialysis	
Short Title	HiLo	
Protocol Number	Pro00100325	
Funding Source	National Institutes of Diabetes and Digestive and Kidney Diseases	
Study Design	Pragmatic, open-label, clinical outcomes trial with individual- level randomization	
Principal Investigator	[name], MMSc	
Study Objectives	
 
To determine whether less stringent control of serum phosphate to target levels of ≥6.5 mg/dl versus the current standard approach of targeting serum phosphate levels of <5.5 mg/dl will result in lower rates of the hierarchical composite outcome of all-cause mortality and all-cause hospitalization among patients with ESRD undergoing hemodialysis.
 
To demonstrate the capacity to conduct a second- generation, large-scale, randomized pragmatic clinical
 
	
Intervention / Comparator Arms	trial that requires individual-level informed consent in partnership with two dialysis provider organizations. High protocol: Target a serum phosphate range of ≥6.5 mg/dl Low protocol: Target serum phosphate of <5.5 mg/dl	
Enrollment Period	24 months	
Duration	45 months	
Dialysis Provider(s)	Outpatient hemodialysis facilities operated by: 1. DaVita, Inc. 2. University of Utah	
Data Coordinating Center	Duke Clinical Research Institute (DCRI)	
Number of Facilities, Patients	100-150 facilities, ~4400 patients	
Main Eligibility Criteria	
 
Dialysis Facility Eligibility
 
Willingness of the medical director, treating nephrologists and dietitians to adopt either the high or low phosphate target ranges for participating patients
 
Willingness of the facility manager to allow dietitians to participate in training and regularly scheduled teleconferences throughout the duration of HiLo
 
Facility dietitian comfort with the phosphate targets and willingness to implement the trial procedures and attend training and teleconferences throughout the duration of HiLo
 
Patient Eligibility
 
Inclusion criteria:
 
Adults ≥18 years
 
	

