## Table 2: Serum Phosphate Thresholds

Arm	Phosphate Target	Action Threshold	Action, Upper Threshold	Action, Lower Threshold
Low	<5.5 mg/dl	≥5.5 mg/dl	Binder therapy	Binder therapy
High	≥6.5 mg/dl	<6.5 mg/dl	increased	decreased

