1. STUDY DETAILS

1.1 Study Objectives

The primary objective of HiLo will be to test the primary and secondary study hypotheses:

Primary hypothesis: Compared to the current standard approach of targeting serum phosphate levels of <5.5 mg/dl, less stringent control of serum phosphate to target levels ≥ 6.5 mg/dl will improve time to all-cause mortality and number of hospitalizations. This hypothesis will be tested using a hierarchical endpoint that prioritizes improvements in all-cause mortality over hospitalizations.

Secondary hypotheses: The trial will test the secondary hypotheses that less stringent control of serum phosphate will result in increased time to death; lower per-person year (PPY) hospitalization rates; and increased serum albumin and protein catabolic rate (PCR), as markers of diet and nutrition.

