2.1.2 In Range (IR) Population

The aim of the IR population is to include the patients that have reached the targeted phosphate levels for the trial. Table 1 in section 4.4.1 below presents the "in range" phosphate range for each treatment arm. Phosphate levels will be measured on a monthly basis for each patient in the trial. Patients that are in range for 75% of their monthly phosphate measures will be included in the IR population.

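### SAP Table 1 counts the Hi arm as in range only above 6.5 mg/dl, while the protocol and SAP 1.1/1.2 set the Hi target at 6.5 mg/dl or above, so the two limits need reconciling

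*SAP*

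**What the plan says.** The Hi target is stated the same way almost throughout. The protocol synopsis has "High protocol: Target a serum phosphate range of ≥6.5 mg/dl", Protocol 4.6 has "The goal is to titrate and maintain serum phosphate to ≥6.5 mg/dl", and the Hi row of Protocol Table 2 (target, then action threshold) reads "High ≥6.5 mg/dl <6.5 mg/dl". Protocol 2.1 and 4.1 agree. So do SAP 1.1 ("less stringent control of serum phosphate to target levels ≥ 6.5 mg/dl") and SAP 1.2. All of these include 6.5 in the target.

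SAP 4.4.1 differs. It says "The target ranges for patients and site average for each arm are provided in Table 1", and the first row of that table, Hi then Lo, is "In range >6.5 <5.5". The next row, *Near range*, runs from 5.5 to 6.5 in both arms, so a Hi value of 6.5 falls there.

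Table 1 is used in two ways. Sites receive a monthly listing of patients outside *In range*. It also defines the analysis sets: SAP 2.1.2 refers to the in-range limits of Table 1 for IR membership (75% of monthly measures), and SAP 2.1.3 defines IR2 in the same way at 50%. SAP 4.5.3 repeats all primary, secondary and additional analyses in IR. SAP section 6 states that no changes in analysis from the protocol are planned.

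**The concern.** A Hi patient with a monthly average of exactly 6.5 has met the target that defines the arm, but the SAP does not count that month as in range. The SAP gives no reason for a stricter limit, and its section 6 implies that none was intended.

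The mismatch is one-sided, because the Lo limit is below 5.5 in both documents. The disputed value is also not at the edge of the Hi distribution: Protocol 4.6 anticipates a Hi mean of 6.5–6.8 mg/dl. Two things are at stake. The first is who appears on the listing sent to sites. The second is who belongs to a pre-specified analysis set, which should not depend on which section a programmer reads.

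**Working it through.** **Step 1. Classify values under each text.** The plan states no figure on this point, so there is none to reproduce.

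| Hi monthly average (mg/dl) | Meets Hi target (protocol, SAP 1.1/1.2) | SAP Table 1, Hi |
|---|---|---|
| 5.4 | no | Out of range |
| 5.5 | no | Near range |
| 6.4 | no | Near range |
| **6.5** | **yes** | **Near range** |
| 6.6 | yes | In range |

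Only 6.5 is treated differently. For Lo, both texts give below 5.5.

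**Step 2. Inputs for the size.** From the documents:
- Hi mean 6.5–6.8 (Protocol 4.6).
- Classification on the average of all measures in a calendar month (SAP 4.4.1).
- Monthly measurement, typically repeated biweekly during titration (Protocol 4.6.1).
- Shortest planned follow-up 27 months (Protocol 4.4).
- IR at 75% (SAP 2.1.2).

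Assumed, because the documents do not give them:
- Normal values, with between-patient SD *b* = 0.6–1.2 and within-patient SD *w* = 0.8–1.2 mg/dl.
- Reporting to 0.1 mg/dl.
- *k* = 1 or 2 measures per month.
- IR membership assessed on the monthly average.

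**Step 3. Share of Hi patient-months at exactly 6.5.** The monthly average lies on a grid of width 0.1/*k*, with total SD *s* = √(*b*² + *w*²/*k*). So P(average = 6.5) ≈ (0.1/*k*) × φ((6.5 − mean)/*s*) / *s*, where φ is the standard normal density.

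- Highest case: *k* = 1, *b* = 0.6, *w* = 0.8, mean 6.5. *s* = √(0.36 + 0.64) = 1.00, giving 0.1 × 0.399 / 1.00 = 4.0%.
- Middle case: *k* = 1, *b* = 0.8, *w* = 1.0, mean 6.65. *s* = √1.64 = 1.28, giving 0.1 × 0.396 / 1.28 = 3.1%.
- Lowest case: *k* = 2, *b* = *w* = 1.2, mean 6.8. *s* = √(1.44 + 0.72) = 1.47, giving 0.05 × 0.391 / 1.47 = 1.3%.

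Over 27 months this is 27 × 0.013 ≈ 0.4 to 27 × 0.040 ≈ 1.1 months per Hi patient.

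**Step 4. Effect on Hi IR membership.** Each patient is given a true level and 27 monthly averages, rounded as above. The patient is in IR if at least 75% of months qualify; 0.75 × 27 = 20.25, so 21 months are needed. Simulated shares of the Hi arm in IR:

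| Mean | *b* / *w* | *k* | Limit >6.5 | Limit ≥6.5 | Difference (points) |
|---|---|---|---|---|---|
| 6.5 | 0.6 / 0.8 | 1 | 17% | 21% | about 4 |
| 6.65 | 1.0 / 1.2 | 1 | 24% | 27% | about 3 |
| 6.8 | 0.6 / 0.8 | 1 | 31% | 37% | about 6 |

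With two measures a month and the three larger SD pairs (0.8/1.0, 1.0/1.2, 1.2/1.2), the difference is about 1.5–2.4 points. Over all combinations it is about 1.5–6 points.

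**Step 5. Sensitivity to follow-up.** With 36 months and SD pairs from 0.6/0.8 to 1.0/1.2, the IR difference is 1.7–6.2 points. For example, at mean 6.65, *b* = 0.8, *w* = 1.0 and *k* = 1, IR goes from 26.7% to 30.6% and IR2 from 56.6% to 61.2%. Lo membership does not move.

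**The case against.** The best case against giving this weight is that it changes nothing important, and much of that stands. SAP 2.1.1 assigns the primary and all major secondary analyses to ITT by assigned arm, so their estimates and tests do not use Table 1. IR is selected on phosphate achieved after randomisation, so its arms can differ under either limit. The anticipated Lo mean (4.8–5.2) is 0.3–0.7 below its limit, whereas the anticipated Hi mean is only 0–0.3 above 6.5. A shift of a few points in Hi membership adds to an imbalance that may exist anyway, and no changed conclusion has been shown.

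A reader might also infer more than the documents support:

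- *That a patient at 6.5 is declared off target, or that sites are told to act.* Table 1 calls 6.5 *Near range*, not *Out of range*, and SAP 4.4.1 attaches no action to the listing. The notifications in Protocol 4.8 concern values repeatedly in an action-required range.
- *That analyses in IR2 are affected.* IR2 membership would change, but SAP 4.5.3 repeats analyses only in IR and assigns none to IR2.
- *That the boundary value is common.* It lies near the centre of the Hi arm, but accounts for only about 1.3–4% of patient-months.
- *That the documents settle which limit is right.* Table 1 also serves as the target range used with sites, so that decision is the sponsor's.

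It could also be suggested that the strict sign is a PDF-reading fault. That is unlikely: *Near range* ends at 6.5, which fits a strict limit, and the inclusive sign survives elsewhere in the SAP.

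The contradiction itself is not rebutted. Two current texts classify the same value differently, and Table 1 is a working threshold.

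**Conclusion.** The inconsistency is real, confined to a Hi monthly average of exactly 6.5 mg/dl, and minor. Such a month meets the stated target but puts the patient on the listing of those outside *In range* and does not count towards IR or IR2. Only the Hi arm is affected.

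The classification conflict follows from the text alone. Its size (about 1.3–4% of Hi patient-months, and about 1.5–6 percentage points of Hi IR membership) rests on the assumed SDs, rounding, number of measures and 27 months. The upper end needs the smallest SDs and a single measure each month; repeated measures bring it down. The ITT primary and major secondary analyses, power and alpha are unaffected.

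**What to change.** Reconcile SAP Table 1 with the Hi target in the protocol synopsis, 2.1, 4.1, 4.6 and Table 2 and in SAP 1.1 and 1.2, with the sponsor confirming the boundary. Use that single boundary in the *In range* and *Near range* rows for Hi, in the IR and IR2 programming, and in the site listing. If a different limit for classification is intended, SAP 2.1.2 and section 6 should say so and give the reason.

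Do this before the IR analyses are run, so that the choice cannot appear to follow the results. The cost is a table cell or two and a line of code. If the listing limit changes, record the date, because sites may already have received listings under the present one.
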